implementation and scalability of the intervention including nurse involvement. Nurses concurred with pts experiences, and suggested strategies to recruit and retain dyads for the study, which are now included in the methodology section of the current grant proposal. Studies 3.6 and 3.7 represent the building blocks for the development of our Recovering Together program and manual. Nurses provided edits and contributed to the iterative development of the manual. These studies also confirm feasibility of conducting the pilot RCT proposed through this R21.

II. SPECIFIC AIMS

The current study has the following objectives:

Aim 1: To determine the feasibility of recruitment, feasibility of program delivery, program credibility, and program satisfaction using evidence-based benchmarks.

Hypothesis 1: We hypothesize that > 75% of the dyads approached will agree to participate.

Hypothesis 2: We hypothesize that > 75% of dyads who start the intervention will complete at least 4 sessions.

Hypothesis 3: We hypothesize that > 75% of participants will report average credibility (Credibility and Expectancy Questionnaire) scores greater than the scale's midpoint.

Hypothesis 4: We hypothesize that > 75% participants will report average satisfaction (Client Satisfaction Scale) scores greater than the scale's midpoint.

Aim 2: To demonstrate a proof of concept that the Recovering Together program can sustainably improve emotional distress [Hospital Anxiety and Depression Scale; HADS], Post Traumatic Symptoms (PTS) [PCL-S], resiliency variables (mindfulness, coping, social support and self-efficacy) and interpersonal factors (interpersonal bond).

Hypothesis 1: We hypothesize that participation in the Recovering Together Program will be associated with a more potent decrease in emotional distress and PTS compared to participation in the educational program (control), and that these improvements will maintain at 3 month follow up.

Hypothesis 2: We hypothesize that Recovering Together Program will be associated with a more potent increase in resiliency variables (mindfulness, coping, social support, self-efficacy) and interpersonal factors (interpersonal bond) compared to participation in the educational program, and that these improvements will maintain at 3 month follow up.

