Participants will be explicitly informed that this intervention is a research study that does not constitute individualized, personal care. The intervention is a broad-based method of training that is not tailored to any particular individual. Should any participant seek formal mental healthcare, study staff will refer them to either MGH Psychiatry, as appropriate.

We will recruit pts with any type of ANI and their cgs, ensuring representation of all NICU diagnoses. All cgs will be recruited within the first week of the pts' hospitalization. Pt's medical team will also alert the research assistant whether they anticipate that the patient might be able to participate in the study at a future point during the hospital stay. In situations where patients are unable to consent due to the severity of the ANI, we will enroll the informal cg and return to enroll the pt as soon as their mental capacity improves. The research assistant will not approach patients who are not mentally or physically capable to participate. This study does not include participants with impaired decision making.

We will not include patients who do not have a caregiver. Informal caregivers will be designated by the health care proxy and verbally confirmed by the patient. Nurses will assist the study team with identifying the patient's health care proxy.

Eligible cases may also be identified by daily screening of Epic admission reports.

The study team will keep track of all pts and cgs approached who refuse to participate (along with reasons for refusal), as well as those who were not approached and reasons why.

When the RA approaches a patient, patients and caregivers will be given the choice of watching a short recruitment video that contains testimonials from previous patients.

The recruitment process was developed and refined through prior research for the past 2 years.

IV. SUBJECT ENROLLMENT

Participants will be referred to the study by the nursing team who will ensure that patients are medically and cognitively able to participate. Eligible dyads will next be screened, consented, and enrolled by the research assistant.

After determining eligibility, study staff will meet with potential dyads to review the informed consent document. Patients who cannot make their mark on the consent form because of lingering symptoms from the ANI can indicate consent by other means, e.g., orally, nodding

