their head, etc. The means by which consent was given by the subject will be documented in the consent form and research record. If cgs cannot be reached in person in the hospital, they will be contacted via phone to complete informed consent. Cgs will be given a copy of the consent form to review while discussing the study over the telephone. We will fax or securely e-mail the consent form prior to obtaining consent. Cgs will return a signed copy of the consent form. After the document has been reviewed, study staff will answer any and all questions the pt or cg may have. Once all questions have been addressed, each member of the dyad will sign the consent form, which will include a description of all study procedures, the option to receive text message reminders, information about potential risks and benefits of participation, and study contact information (including that of the IRB) in case questions arise at a later time. The consent form will also explicitly state that study participation is voluntary, and that participants may refuse to answer any questions that make them uncomfortable, and may discontinue participation at any time. In addition, participants will be assured that withdrawal from the study will not compromise their medical care in any way.

As informed consent is a continuous process, participants will be given a copy of the signed informed consent document, and will be invited to ask questions about their participation at any point over the course of the study.

Following a study enrollment and baseline assessment, dyads will be randomly assigned to either the newly developed psychosocial intervention or to the educational program (control) using a random number sequence generator to ensure comparability between groups. We will document time between assessment and intervention initiation, and analyze as a predictor of study outcomes as needed. Randomization will be developed by the statistician, without any input from the rest of the team.

V. STUDY PROCEDURES

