After enrollment, participants will complete study assessments. All subjects will be given baseline psychological and behavioral assessments that will assess depression, anxiety, PTS symptoms, and other psychological constructs. Assessments will be administered online, using the REDCap system. Subjects may choose to fill out these questionnaires on-site, or to fill them out at home on a personal computer or other Internet-equipped device. This assessment includes demographic information and a battery of psychological questionnaires. We will also collect information about important clinical variables including duration of acute hospitalization. All questionnaires are itemized below:

Administered at Baseline Only:

Demographics

Prior Mental Health History questions

Credibility Questionnaire

Administered at Baseline, Post-Intervention, and Follow-up:

Medical history information from LMR (i.e., prior ANI status, current psychotropic meds, comorbid medical conditions, etc.)

Post-Traumatic Stress Disorder Checklist (PCL-S)²⁹

Hospital Depression and Anxiety Scale (HADS)³⁰
 Measure of Current Status Part A (MOCS-A)³¹
 The Cognitive and Affective Mindfulness Scale (CAMS)³²
 World Health Organization Quality of Life (WHOQOL-BREF)³³
 Dyadic Relationship Scale (DRS)
 Experience in Close Relationships – Relationship Structure (ECR-RS)

Administered Post-Intervention and Follow-up Only:
 Client Satisfaction Questionnaire (CSQ-3)³⁴

The study staff will complete the following questionnaires to assess symptom severity for each patient at all 3 timepoints (baseline, post intervention and follow up):

Modified Rankin Scale (mRS)³⁵ [Pts only]
 Barthel Index³⁶ [Pts only]

After completing the baseline assessments, dyads will be randomized to either the newly developed psychosocial intervention or to treatment as usual.

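### Programme credibility, a primary outcome, is scheduled only before randomisation, so Aim 1 Hypothesis 3 cannot show that Recovering Together is credible to those assigned to it

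*Combined protocol and SAP*

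**What the plan says.** Section II (Specific Aims) sets Aim 1 as: "To determine the feasibility of recruitment, feasibility of program delivery, program credibility, and program satisfaction using evidence-based benchmarks". H3 under that aim requires more than 75% of participants to score above the scale midpoint on the Credibility and Expectancy Questionnaire. It names neither an arm nor a time point. Sections II and VI both class credibility as a primary outcome, and question 1 of Section VI (Biostatistic Analysis) asks it of the skills-based intervention.

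The only itemised schedule is in Section V (Study Procedures), introduced by "All questionnaires are itemized below". Under the heading "Administered at Baseline Only" it lists demographics, prior mental health history and the "Credibility Questionnaire". The satisfaction scale (CSQ-3) is listed separately, for post-intervention and follow-up.

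Two sections fix the order of events. Section IV (Subject Enrollment) says: "Following a study enrollment and baseline assessment, dyads will be randomly assigned". Section V says: "After completing the baseline assessments, dyads will be randomized to either" one arm or the other.

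On what participants know by then, Section IV describes a consent form "which will include a description of all study procedures". Under Recruitment, Section III says they are told: "The intervention is a broad-based method of training that is not tailored to any particular individual".

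**The concern.** At the scheduled moment a participant has read a description of the trial but does not know which programme they will get and has attended no session. They can form an expectation, but they cannot rate the programme they were assigned. The readable text also does not say which of the two programmes is being rated, and the questionnaire is not reproduced.

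H3 could therefore pass or fail with no rating from anyone who had been introduced to Recovering Together as their own programme. The benchmarks are the main product of this pilot, and H3 is one of four under Aim 1. A reader deciding whether to take the programme to a larger trial would see a credibility result that does not answer the question in Section VI, and once the data are collected the missing rating cannot be recovered.

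**Working it through.** **Inputs**
- Planned sample (Section VI): 80 dyads, 160 participants; 40 dyads, 80 participants per arm.
- Attrition allowed for (Section VI): 25%, leaving 30 dyads per arm.
- Benchmark (Section II, H3): strictly more than 75%.
- Timing of the credibility rating (Section V list): baseline only.
- Timing of randomisation (Sections IV and V): after baseline.

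**The plan's own figure.** 30 / (1 − 0.25) = 40 dyads per arm, as stated. The sample size is not in dispute and does not change below.

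**Order of events as written.** Consent, then baseline including the credibility form, then randomisation, then sessions.

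**Ratings by position relative to allocation**
- Ratings made after allocation: 0 of up to 160.
- Ratings from participants who will be assigned to the control: 80 / 160 = 50%.

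**Can analysis by arm rescue H3?** No. Allocation is random and comes after the rating, so the Recovering Together subset is a random half of one pool. Any difference between arms in these ratings would be chance. The subset has the same meaning as the whole: expectation before allocation.

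**What the benchmark would require after the change.** With n in the denominator, the smallest count strictly above 75% is floor(0.75 × n) + 1. In the Recovering Together arm, with all 80 rated, this is 60 + 1 = 61, and 61/80 = 76.25%; 60 of 80 is exactly 75% and fails.

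The documents do not give the number who would not reach the rating. Taking 4 or 8 of 80 as an assumption for illustration:

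| Unrated (assumed) | Rated | Pass mark among those rated | Pass mark if unrated count as not above midpoint |
|---|---|---|---|
| 0 | 80 | 61 (76.25%) | 61 (76.25%) |
| 4 | 76 | 58 (76.3%) | 61 (80.3% of those rated) |
| 8 | 72 | 55 (76.4%) | 61 (84.7% of those rated) |

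The two counting rules differ by 3 participants at 4 unrated and by 6 at 8 unrated, so the rule needs to be set beforehand. These counts describe the proposed rating; the size of the defect itself is the 0 of 160.

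**The case against.** **A prospective rating may be what was intended.** The instrument covers expectancy as well as credibility, H3 speaks of participants without naming an arm, and a baseline rating is free of allocation and clinician effects. Participants also know something by then, from consent and from an optional recruitment video with testimonials. If the form names Recovering Together, a baseline rating does say something about its prospective credibility. This part stands, and it is a good reason to keep a baseline rating as description. It does not supply the credibility of the programme to those assigned to it, and the text never says that Recovering Together is what is rated.

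**Other text can be read as repeating the questionnaire.** Section V says the post-treatment battery matches the baseline one with the CSQ-3 added, and Section VI says measures are collected at all three time points. The protocol has no rule on which text prevails. But neither sentence names credibility, and the baseline-only heading is specific; it also covers demographics, which no one would repeat. On the other reading, H3 would have several possible time points and none designated. Either way the text needs correcting.

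**A session-1 rating has costs.** A rating at the end of session 1 mixes the rationale with the clinician and the first session's content, and omits those who never attend. Both points are fair. Session 1 is only one option, and a rating taken once the rationale is explained but before session content would lessen the first problem.

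**Other measures cover acceptability.** Satisfaction and session completion are measured after exposure, but neither measures credibility.

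**Conclusion.** The concern holds. As scheduled, every credibility rating precedes allocation, so H3 measures pre-allocation expectancy and cannot show that Recovering Together is credible to the people assigned to it. The size is 0 of up to 160 ratings after allocation, with one of the four Aim 1 benchmarks affected. The other three benchmarks and the sample size are untouched.

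The conclusion rests on two readings: that the itemised list in Section V governs over the general sentences in Sections V and VI, and that the stated order of baseline and randomisation is followed. It is confined to the readable text, since the consent form and the questionnaire are not reproduced. It should be fixed before data collection, because later analysis cannot supply the missing ratings.

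**What to change.** - Give the existing Credibility and Expectancy Questionnaire once after randomisation, in both arms, when the rationale of the assigned programme has been explained. In-hospital session 1 is a convenient point, since both arms have two in-person hospital sessions.
- State on the form that the assigned programme is what is rated, in neutral words (the programme you were assigned), so that the blinding of patients intended in Section V is kept.
- In Aim 1, name this rating as the H3 time point and score H3 in the Recovering Together arm. Report the control arm alongside as description.
- State in advance how randomised participants without a rating are counted, and report their number by arm.
- Label any baseline rating as descriptive only.
- Align the general sentences on repeated measures in Sections V and VI with the itemised list.

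The cost is small: one existing questionnaire is moved, or repeated once, at a contact both arms already have, with short edits to Sections II, V and VI. The drawback is that participants who do not reach the rating give none, which is why the counting rule must be written down first.

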Clinically significant emotional distress in one member of the dyad at hospitalization predicts chronic emotional distress in at least 1 of the dyad members 3 and 6 months later⁵⁵. Our team has an ongoing prospective study of dyads with ANI. Retention rates for dyads due for assessments at 3 and 6 months thus far are 84% and 91% for pts and 87.7% and 95.7% for cgs, confirming our ability to retain post-ANI participants. Within each dyad, if one member screens in for clinically significant symptoms for any diagnosis (i.e., depression, anxiety or PTSD) at hospitalization there is good sensitivity and specificity that one member of the dyad will endorse clinically significant symptoms 3 months later. This study shows a reliable method for identifying dyads of patients at risk for chronic heightened emotional distress by identifying dyads in which either the pt or cg screens in for heightened emotional distress (symptoms of depression, anxiety or PTSD).

Caregiver gender moderates the prospective association of resiliency factors to emotional distress⁸⁷. This study found that at the time of admission resiliency factors have main effects on emotional distress, with no differences by cg gender. However, significant interaction effects emerged prospectively such that male cgs with high mindfulness at baseline demonstrated lower levels of emotional distress at 3 and 6 months later than did males with low mindfulness ($p = 0.026$ and $p < 0.013$). Similarly, women cgs with high intimate bond at baseline reported the lowest levels of depression symptoms 3 and 6 months later ($p < 0.020$). This study confirmed the need to assess and address resiliency factors early in the recovery process, and identified important gender differences to be accounted for in intervention development.

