Our primary aim focuses on trial feasibility, acceptability, credibility and preliminary effect. In pilot studies, ≥ 30 participants are recommended per group to establish feasibility and detect larger effect sizes for ≥ 1 outcome. We plan to recruit 80 dyads (160 participants), 40 dyads (80 participants) per arm to establish feasibility, acceptability, credibility and estimate effect size for emotional distress variables (primary quantitative outcomes). Assuming attrition of over 25% (in excess of what we experienced in our preliminary studies), we will have the necessary 30 dyads (60 participants) per arm. This

size is considered to yield stable estimates of M/SDs based on prior behavioral trial recommendations. Effect sizes from this study may overestimate power in future sample calculations. We chose study measures based on our theoretical frameworks, strong psychometric properties in studies of patients with ANI, and feasibility work in our prior work with ANI dyads. Feasibility will be reported as the percentage of patients enrolled in the study who complete at least 75% of the intervention sessions. Demonstration of feasibility will be assessed by the number of individuals who drop out of the study prior to completing the post- intervention assessment and the rate of missed sessions. If drop-out rate or missed-session rate exceeds 25%, revisions to the intervention may be needed. We will also report number of patients approached, enrolled, randomized and who completed time 2 and time 3 to determine feasibility.

2) Is the psychosocial skills-based intervention effective for pts and cgs in the ICU?

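### The sample-size sentence is false as worded: 40 dyads per arm leave 30 only if attrition is at most 25%, and joint dyad retention is not reported

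*Combined protocol and SAP*

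**What the plan says.** The sample-size argument is in the combined protocol and SAP, Section VI (Biostatistic Analysis), under the first question.

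- It starts from a rule of thumb counted in participants: "In pilot studies, ≥ 30 participants are recommended per group to establish feasibility and detect larger effect sizes for ≥ 1 outcome".
- It sets recruitment: "We plan to recruit 80 dyads (160 participants), 40 dyads (80 participants) per arm".
- It sets the loss allowance and what it leaves: "Assuming attrition of over 25% (in excess of what we experienced in our preliminary studies), we will have the necessary 30 dyads".
- It gives the participant count as well: "we will have the necessary 30 dyads (60 participants) per arm".

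No power, alpha, effect size or standard deviation enters the calculation.

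The only retention figures from earlier work are in Section I (Background and Significance), in the account of the ongoing prospective dyad study. They are given separately for patients and caregivers: "at 3 and 6 months thus far are 84% and 91% for pts and 87.7% and 95.7% for cgs". The proportion of dyads with both members retained is not given.

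**The concern.** The sentence pairs an attrition assumption with a remaining sample size, and the two do not fit. Thirty out of 40 is what remains at exactly 25% loss, while the text assumes more than that. Together with the remark that the allowance exceeds past experience, the wording suggests a safety margin that the numbers do not contain.

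There is also a question of unit. The sentence counts dyads, and dyads are what the trial randomises, but the past experience it appeals to is reported by member. A dyad can be lost through either member, so dyad loss can exceed the loss in either group.

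At stake is the credibility of a size that the plan itself calls necessary, and whether the retention assumption is stated correctly in a trial whose primary purpose is feasibility.

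**Working it through.** **Inputs**

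- Recruited per arm: 40 dyads, 80 participants (Section VI).
- Attrition: above 25%, no exact value (Section VI).
- Required per arm: 30 dyads, 60 participants (Section VI).
- Earlier retention (Section I): patients p = 0.84 at 3 months and 0.91 at 6 months; caregivers c = 0.877 and 0.957.

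**Step 1. Reproduce the plan's figure.** Remaining = N × (1 − d). At d = 0.25, 40 × 0.75 = 30. In reverse, 30 / 0.75 = 40. The recruitment target and the form of the inflation are both correct at 25%. Counting participants puts the boundary in the same place: 80 × 0.75 = 60.

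**Step 2. Apply the assumption as written.**

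| Attrition | 40 × (1 − d) | Whole dyads | Participants in those dyads |
|---|---|---|---|
| 25% | 30.0 | 30 | 60 |
| 26% | 29.6 | 29 | 58 |
| 27.5% | 29.0 | 29 | 58 |
| 30% | 28.0 | 28 | 56 |

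No value above 25% leaves 30.

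**Step 3. Check the bracket by member.** Patient loss is 1 − 0.84 = 16% and 1 − 0.91 = 9%. Caregiver loss is 1 − 0.877 = 12.3% and 1 − 0.957 = 4.3%. All are below 25%.

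**Step 4. Check the bracket by dyad.** Assume that a dyad counts only if both members are retained, and that the two rates at each time point share a denominator. Joint retention then lies between p + c − 1 (losses never in the same dyad) and min(p, c) (losses overlap as far as possible). It equals p × c if losses are independent.

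| Time | Case | Joint retention | Dyad loss | Left of 40 |
|---|---|---|---|---|
| 3 months | Disjoint | 0.84 + 0.877 − 1 = 0.717 | 28.3% | 28.7 |
| 3 months | Independent | 0.84 × 0.877 = 0.737 | 26.3% | 29.5 |
| 3 months | Overlapping | 0.84 | 16.0% | 33.6 |
| 6 months | Disjoint | 0.91 + 0.957 − 1 = 0.867 | 13.3% | 34.7 |
| 6 months | Independent | 0.91 × 0.957 = 0.871 | 12.9% | 34.8 |
| 6 months | Overlapping | 0.91 | 9.0% | 36.4 |

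**Step 5. Find the correlation that brings 3-month dyad loss to 25%.** The within-dyad (phi) correlation of retention at joint retention 0.75 is (0.75 − 0.84 × 0.877) / √(0.84 × 0.16 × 0.877 × 0.123) ≈ 0.11. Above that value, 3-month dyad loss is below 25%.

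**The case against.** The best defence is that this is one misplaced word. The figures 40 and 30 agree exactly at 25%. The rule cited is 30 participants per group, and 28 or 29 dyads still supply 56 or 58 participants. No power calculation depends on 30 dyads. All of this stands, and it limits the weight of the point. It does not make the sentence true, and the plan itself calls 30 dyads necessary.

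On the bracket, the defence is that every reported member-level loss is below 25%, that the 6-month rates cap dyad loss at 13.3%, and that Section VI describes drop-out by counting individuals and names analyses that do not require both members. The comparison is therefore supported by member. For dyads it remains open. The 6-month cap takes those rates at face value, yet they are higher than the 3-month rates and cover dyads due for assessment so far, so the denominators may differ. Nor is the 3-month rate a direct match. Section I counts from hospitalisation, whereas this trial's last assessment falls 3 months after the programme ends.

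A reader might draw three stronger conclusions, and the documents support none of them.

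- *The sample size was miscalculated.* It was not: the calculation is right at 25%, and the description of the boundary is wrong.
- *The team's own data show dyad loss above 25%.* They do not: the 3-month range runs from 16.0% to 28.3%, and a modest within-dyad correlation brings it below 25%.
- *The assumption conflicts with the feasibility rule* "If drop-out rate or missed-session rate exceeds 25%, revisions to the intervention may be needed". It does not: that rule concerns drop-out before the post-intervention assessment or missed sessions, and a cautious planning allowance is not a forecast that the rule will be met.

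**Conclusion.** The point holds as a wording error together with an unreported figure. As written, the sentence fails for every attrition value it covers, and the design has no margin beyond 25%. The shortfall is 1 to 2 dyads per arm for attrition up to 30%. The claim to exceed past experience is sound for individual members and undetermined for complete dyads. That second part rests on two assumptions that the documents do not settle: that losing either member loses the dyad, and that the member rates share a denominator at each time point. The point changes no analysis, decision rule or recruitment target.

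**What to change.** Reword the sentence to say that, with an allowance of up to 25% attrition among dyads, 30 dyads or 60 participants will remain in each arm. Then do one of two things with the bracket: give the proportion of dyads in the prospective study with both members retained, with its time point and denominator, or say that the comparison refers to attrition among individual members.

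The cost is one sentence, plus one tabulation if the joint figure is added. The stated allowance becomes slightly less favourable. Recruitment can stay at 40 dyads per arm. Only if the sponsor wants to keep 30 dyads under heavier loss would the target move: 30 / 0.74 = 40.5, so 41 per arm at 26%, and 30 / 0.70 = 42.9, so 43 at 30%. The cited rule does not require this.
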